9 STUDY CALENDAR

			W	eek	(+/·	- 2 d	lays	5)			Week (+/- 7 days)		
Examination	Screenin g ¹	Baseline ^{1,} 2 Day 1	1	2	3	4	5	6	7	8	9	End of study ⁵	22
Informed consent	Χ												
Eligibility criteria	X												
Concomitant medications	X											X	
Questionnaires ³													
• CIPN-20	X											X	X
• BPI		X										X	X
CIPN-R-ODS		X										X	X
• MAIA-2		X										X	X
• Demographics		X											
Acupuncture treatment (AT) ⁴				X X	X X	X	X	X	X	X	X		
fMRI ⁶			X									X	

¹ Screening visit and Baseline visit can occur on the same day.

- ² Day 1 (Baseline) should occur within 2 weeks of the screening visit.
- ³ Questionnaires include: (See Appendices).
- ⁴ Acupuncture treatment (AT) will occur at the Wellness & Integrative Health Center at HCI. Twice a week treatments will occur within 4 business days.
- ⁵ End of study visit should occur within one week of final acupuncture treatment.
- ⁶ Must be within 9 days of baseline visit. If participant prefers, first study fMRI can be same day as first AT treatment.

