Clinical data including current medications and medical history and fall rates will be gathered. Questionnaires (BPI, CIPN-20, CIPN-R-ODS, MAIA-2, Demograhpics) will be completed in person or emailed to patients via REDCap. Reminder calls and AT appointments will be scheduled by HCI Wellness and Integrative Health Center personnel in conjunction with a SC. The SC will aid participants in scheduling fMRI appointments online. AT treatments will occur within 7 days/4 business days in general. If participant prefers the first study fMRI and first AT appointment can occur same day, with the fMRI procedure occurring prior to AT treatment.

Follow up Visits:

Participants will receive 10 sessions of AT: twice per week for 2 weeks, thereafter once per week for six weeks, with a total of 10 treatments during a two-month course. Each session will last 45-60 minutes, with acupuncture needles retained 30-40 minutes. A minimum of 8 treatments must be received by each participant with no more than 9 days' gap between weekly treatments permitted (sessions 5-10). Concurrent medications are allowed as prescribed and will be tracked in the study and analyzed as potential confounders.

Final Visit:

Participants will undergo examination within one week of AT completion. This will include the fMRI scan and questionnaires. Compensation for participation will be offered at this visit.

Procedures:

Measures: Questionnaires will be completed in person or emailed to patients via REDCap at baseline and study conclusion, as well as at a 3-month follow-up. *Primary Endpoints:* Mean enrollment, percentage completion rate of all study procedures, frequency count of serious adverse events, and percentage of enrolled participants completing questionnaires will be calculated. Data will be collected via REDCap, stored in the Research Subject Registry (RSR) and analyzed with SPSS.

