11.2 Safety

The DSMC will consist of the appropriate Huntsman Cancer Institute (HCI) DSMC members.

Overall safety of this study will be assessed using the CTCAE (NCI Common Terminology Criteria for Adverse Events) version 5.0 and the following safety and tolerability endpoints will be used:

-incidence of treatment-emergent adverse events associated (TEAE's) with acupuncture- known TEAE's detailed below.

Patients will be instructed to disclose all study-related side-effects, symptoms or AEs. Potential adverse effects of acupuncture treatment include: Bruising Bleeding Needle shock Pre-syncope (Dizziness) Diaphoresis (Sweating) Nausea and Vomiting Loss of consciousness

The main side effects of acupuncture include a slightly increased risk of minor bruising and bleeding and rarely infection. Needle shock, a vaso-vagal response to needle insertion, occurs about 5% of the time usually during the first or second treatment. Patients may become faint, diaphoretic, nauseated and occasionally lose consciousness. These are often reversible by removing the acupuncture needles and laying the patient supine.

-incidence of procedure-related adverse events associated with fMRI (source: FDA)

MR images are made without using any ionizing radiation, so patients are not exposed to the harmful effects of ionizing radiation. But while there are no known health hazards from temporary exposure to the MR environment, the MR environment involves a strong, static magnetic field, a magnetic field that changes with time (pulsed gradient field), and radiofrequency energy, each of which carry specific safety concerns:

• The strong, static magnetic field will attract magnetic objects (from small items such as keys and cell phones, to large, heavy items such as oxygen tanks and floor buffers) and may cause damage to the scanner or injury to the patient or medical professionals if those objects

become projectiles. Careful screening of people and objects entering the MR environment is critical to ensure nothing enters the magnet area that may become a projectile.

- The magnetic fields that change with time create loud knocking noises which may harm hearing if adequate ear protection is not used. They may also cause peripheral muscle or nerve stimulation that may feel like a twitching sensation.
- The radiofrequency energy used during the MRI scan could lead to heating of the body. The potential for heating is greater during long MRI examinations.

Acupuncture Schedule Adjustments

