
The main toxic effects of acupuncture include a slightly increased risk of minor bruising and bleeding and rarely infection. Needle shock, a vaso-vagal response to needle insertion, occurs about 5% of the time usually during the first or second treatment. Patients may become pre-syncopal, diaphoretic, nauseated and occasionally lose consciousness. These symptoms are easily reversible by removing the acupuncture needles and laying the patient supine. There are no universal guidelines in patients with lymphoedema however there may be hospital, academic medical center, or department specific guidelines. These concerns can adequately be addressed by the Study Acupuncturist as toxic effects of acupuncture are taught in all acupuncture schools.

Reporting adverse events and referrals for patient care

During the study, all study patients will be under the care of either a medical oncologist or a surgical oncologist. If any abnormalities or problems, including possible study related adverse events (AE) or reportable serious adverse events(SAEs), are detected during screening, subsequent measurements, or study activities, the patient will be referred back to their medical provider for appropriate care. The SC and study primary investigators (PIs) will be responsible for recording and reporting any intervention related AEs and reportable SAEs. The possible routes of referral are as follows:

a. Abnormality/problem detected during screening and subsequent clinic visits: The SC will notify and discuss with the study PIs. The responsible site investigator as appropriate will refer the patient to their medical provider. The SC and study PIs will record and report any study-related AEs and reportable SAEs as appropriate.

b. Abnormality/problem detected during telephone contact: The SC will refer the patient to their medical provider and the responsible site investigator as appropriate. The SC and study PIs will record and report AEs and reportable SAEs as appropriate.

c. Abnormality/problem detected during acupuncture session: The Study Acupuncturist will notify and discuss with the responsible site investigator. The SC will be notified and the SC and the responsible site investigator as appropriate will refer the patient to their medical provider. The SC and study investigators will record and report as appropriate.

More on adverse event procedures are outlined in section 16.4.1

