16.4.1 Adverse Events (AE)

There is no protocol-directed administration of systemic therapy in this nonpharmacologic study; patients will be taking standard of care anti-cancer therapy prescribed by their treating oncologist. The study-specific AE reporting plan detailed below will be followed. The PI will determine the attribution/relatedness of each AE. Any AEs with a *causal* relation to the research will be graded for severity and seriousness, and followed to either resolution or until the 3-month post follow-up (whichever comes first).

Subjects will receive a systemic treatment regimen for their cancer during study participation. Since such routine interventions and treatment may influence the study results, information regarding the concomitant medications will be collected but not reported to the IRB.

Potential AEs of acupuncture treatment include:

- Excessive and/or unusual bruising
- Excessive and/or unusual bleeding
- Needle shock
- Pre-syncope (Dizziness)
- Diaphoresis (Sweating)
- Nausea and Vomiting

Loss of consciousness

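### Related adverse events are to be followed to 3 months, but no scheduled contact specifies an adverse-event enquiry, and after end of study the only contact is four questionnaires that may be emailed

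*Combined protocol and SAP*

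**What the plan says.** - **Follow-up promised.** Section 16.4.1: "Any AEs with a *causal* relation to the research will be graded for severity and seriousness", and these events are "followed to either resolution or until the 3-month post follow-up (whichever comes first".
- **How events come to light.** Section 11.2: "Patients will be instructed to disclose all study-related side-effects, symptoms or AEs". The same section gives referral routes for three situations: "Abnormality/problem detected during screening and subsequent clinic visits", "Abnormality/problem detected during telephone contact", and a problem found at an acupuncture session. The coordinator and principal investigators (PIs) record and report. Patients stay under an oncologist's care during the study.
- **What is scheduled.** The Section 9 calendar has rows for consent, eligibility, concomitant medications, questionnaires, acupuncture treatment (AT) and fMRI. Its week-22 column marks only CIPN-20, BPI, CIPN-R-ODS and MAIA-2.
- **End of study.** Section 9: "End of study visit should occur within one week of final acupuncture treatment". Section 10 says of this visit: "This will include the fMRI scan and questionnaires". Section 7.1 adds a study interview, medical history, current medications and fall rates.
- **Mode at 3 months.** Section 10: "Questionnaires will be completed in person or emailed to patients via REDCap at baseline and study conclusion, as well as at a 3-month follow-up".
- **Use of the safety data.** Sections 1.1, 11.1 and 12 make the absence of any AT-related serious AE (SAE) a primary feasibility criterion. Section 11.2 makes the incidence of treatment-emergent AEs a safety endpoint.

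**The concern.** The plan sets a follow-up horizon for AEs but does not say at which contact anyone asks about them. Capture is passive, and it is filtered before it reaches the study team: a woman is told to disclose what is study-related, so she judges relatedness first, although Section 16.4.1 gives that judgement to the PI. The routes in Section 11.2 say who is told once a problem has been found. They do not say when anyone looks for one.

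At stake is how two safety results are read. Without a standard question, a zero count of related SAEs, or a low incidence of treatment-emergent AEs, mixes two explanations: few events, or few enquiries. Section 2 describes the pilot as groundwork for a randomised trial, so these results will be carried forward.

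**Working it through.** **1. Does the calendar agree with a 3-month follow-up?** Sessions: 2 × 2 + 6 × 1 = 10, in calendar weeks 2 to 9. End of study is within one week of the last session, so in weeks 9 to 10. Then 9 + 13 = 22 and 10 + 12 = 22. The week-22 column therefore matches the 3-month label.

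**2. How long is the stretch after end of study?** 22 − 10 = 12 weeks to 22 − 9 = 13 weeks. With the ±7-day window at week 22, it runs from 21 − 10 = 11 to 23 − 9 = 14 weeks.

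**3. What does each contact specify?**

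| Contact | Scheduled content | AE enquiry specified |
|---|---|---|
| AT sessions, weeks 2–9 | Treatment; Section 11.2 routes problems detected there | None |
| End of study, weeks 9–10 | fMRI, questionnaires, medications; Section 7.1 adds interview, medical history, falls | None, though these may bring events out |
| Week 22 | Four questionnaires, in person or emailed | None |

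As reproduced in Appendices A to D, none of the four instruments asks about new events, hospital admission, infection, bleeding or the outcome of an earlier event. The CIPN-20 item on dizziness after standing overlaps a listed acupuncture AE, but it is scored as a neuropathy symptom.

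**4. What does zero in 20 show?** With full capture, the one-sided 95% upper bound is 1 − 0.05^(1/20) = 13.9%. If only a fraction c of events is captured, zero events bounds p × c rather than the true rate p, and the chance of observing zero is (1 − p × c)^20. The documents give neither p nor c, so these values are assumptions to show direction only:

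| True rate p | c = 1 | c = 0.75 | c = 0.5 |
|---|---|---|---|
| 1% | 0.82 | 0.86 | 0.90 |
| 10% | 0.12 | 0.21 | 0.36 |

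Zero is already weak evidence at this sample size, and incomplete capture makes it weaker. No sample size, alpha or power figure is affected.

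**The case against.** The strongest reply has four parts.

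- **The 3-month sentence governs known events.** It covers AEs already identified and judged causal. Staff can follow such an event by an unscheduled call or visit, and Section 11.2 names telephone contact. This stands. A reader might infer that the promised follow-up cannot be delivered; the documents do not support that. What is missing is a scheduled contact that provides for it.
- **End of study is more than scans and questionnaires.** The Section 7.1 interview, history, medications and fall rates could reveal an admission or an infection. This also stands, so it would be wrong to infer that the team learns only of events in the treatment room or those a woman volunteers. Still, none of it is framed as an AE enquiry, and nothing like it is scheduled at week 22.
- **Most listed acupuncture AEs are immediate.** Needle shock is put at about 5%, usually in the first or second treatment, where the acupuncturist would see it. Its frequency therefore says nothing about the gap and is not used here. Infection, which Section 11.2 calls rare, is the better example, because it can appear after a woman has left, including after the last session.
- **Proportionality.** This is a 20-woman, low-risk pilot with quarterly DSMC review of AEs and at least annual audit (Section 16.3), and an AE question might sit in case report forms not shown here. That argues for a light remedy. It does not remove the gap, since the DSMC can review only what has been recorded.

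**Conclusion.** The point holds as a gap in ascertainment. Follow-up of related AEs to 3 months is promised, but no scheduled contact specifies an AE enquiry. The gap is clearest in the roughly 12 weeks from end of study to week 22, with one scheduled contact and no AE item. Late related events may be missed, and events open at end of study may lack a documented outcome.

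The number of events that would be missed cannot be derived from the documents, and nothing shows that these later weeks carry the same risk as the treatment weeks.

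The gap may be wider for women with fewer than 8 sessions. Section 7.4 drops them from the study without saying whether their AE follow-up continues, and a woman who stopped because of an AE could be among them.

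The conclusion assumes that the machine-read calendar is complete as to its rows and that no separate AE form already asks the question.

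**What to change.** - Add an AE row to the Section 9 calendar, with one short, standard, non-leading question at each AT session and at the end-of-study visit. It should cover all events since the last contact and leave relatedness to the PI.
- Add a few items to the week-22 REDCap form: new events, hospital admission, and the outcome of any open event. Add a coordinator call only for women with an open event or no reply.
- State in Section 7.4 or 16.4.1 that women dropped for having fewer than 8 sessions receive the same AE follow-up.

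All of this except the occasional call, and contact with dropped women, uses contacts that already exist. The cost is a few minutes per contact and a higher recorded AE count, which the report should attribute to active enquiry. Sample size, analysis methods and treatment do not change.

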16.4.2 Serious Adverse Event (SAE)

AE's which are determined by the PI to be both attributable to study intervention and serious will be reported to the DSMC and/or the IRB as appropriate (refer to section 16.5 for reporting requirements). An AE is considered serious when it results in one or more of the following:

- Death
- Initial or prolonged hospitalization
- Life threatening event
- Disability or permanent damage
- Congenital Anomaly/Birth defect
- Other important medical event which is deemed serious by the PI

16.5 SAE Reporting Requirements

SAEs must be reported to the DSMC and/or the IRB according to the requirements described below:

DSMC Notifications:

- All SAEs which are attributable to study intervention will be reported to the DSMC.
- A MedWatch 3500A form* must be completed and submitted to [contact] as soon as possible, but no later than 24 hours from first knowledge.
- An HCI Research Compliance Officer (RCO) will process and submit the MedWatch form to the proper DSMC member as necessary for each individual study.
- The RCO will summarize and present all reported SAEs according to the Data and Safety Monitoring Plan at the quarterly DSMC meeting.

IRB Notification:

• Events meeting the University of Utah IRB reporting requirements (http://www.research.utah.edu/irb/) will be submitted through the IRB's electronic reporting system within 10 working days.

*Medwatch 3500A form can be found at

http://www.fda.gov/downloads/Safety/MedWatch/HowToReport/DownloadForms/ucm0827 28.pdf

16.6 **Reporting of Pregnancy**

Although pregnancy is not considered an adverse event, it is the responsibility of investigators or their designees to report any pregnancy or lactation in a subject as an SAE. Pregnancies or lactation that occurs during the course of the trial or with 30 days of completing the trial or starting another new anticancer therapy, whichever is earlier, must be

reported to the DSMC, and IRB. All subjects and female partners who become pregnant must be followed to the completion/termination of the pregnancy. Pregnancy outcomes of spontaneous abortion, missed abortion, fetal death, intrauterine death, miscarriage and stillbirth must be reported as serious events.

16.7 **Protocol Amendments**

Any amendments or administrative changes in the research protocol during the period, for which the IRB approval has already been given, will not be initiated without submission of an amendment for IRB review and approval.

These requirements for approval will in no way prevent any immediate action from being taken by the investigator in the interests of preserving the safety of all patients included in the trial.

16.8 **Protocol Deviations**

A protocol deviation (or violation) is any departure from the defined procedures and treatment plans as outlined in the protocol version submitted and previously approved by the IRB. Protocol deviations have the potential to place participants at risk and can also undermine the scientific integrity of the study thus jeopardizing the justification for the research. Protocol deviations are unplanned and unintentional events.

Because some protocol deviations pose no conceivable threat to participant safety or scientific integrity, reporting is left to the discretion of the PI within the context of the guidelines below. The IRB requires the **prompt reporting** of protocol deviations which are:

- Exceptions to eligibility criteria.
- Intended to eliminate apparent immediate hazard to a research participant or
- Harmful (caused harm to participants or others, or place them at increased risk of harm including physical, psychological, economic, or social harm), or
- Possible serious or continued noncompliance

16.9 FDA Annual Reporting

This study is Investigational New Drug (IND) exempt therefore there are no annual reporting requirements to the FDA.

16.10 Clinical Trials Data Bank

The study will be registered on http://clinicaltrials.gov

16.11 Record Keeping

Investigator records shall be kept until 2 years after the investigation is discontinued.

Appendix A: CIPN-20

20 Items are scored 1 to 4 with 1 representing "not at all" and 4 "very much." Maximum score is 100. Higher scores indicate worse CIPN.

EORTC QLQ-CIPN20

Sensory symptoms and problems

- 1. Tingling fingers or hands?
- 2. Tingling toes or feet?
- 3. Numbness in fingers or hands?
- 4. Numbness in toes or feet?
- 5. Aching or burning pain in fingers or hands?
- 6. Aching or burning pain in toes or feet?
- 9. Trouble standing or walking?
- 10. Trouble distinguishing hot and cold water?
- 18. Trouble hearing?

Motor scale

- 7. Cramps in hands?
- 8. Cramps in feet?
- 11. Trouble holding a pen making writing difficult?
- 12. Trouble handling small objects (e.g. buttoning a blouse)?
- 13. Trouble opening jar/bottle due to loss of strength in hands?
- 14. Trouble walking because your feet come down to hard?
- 15. Trouble walking stairs or standing up from a chair due to weakness in legs?
- 19. Only for those driving cars: trouble driving due to use of pedals?

Autonomic scale

- 16. Dizziness after standing up?
- 17. Blurry vision?
- 20. Only for males; Trouble getting or maintaining an erection?

Appendix B: CIPN-R-ODS

Each item is rated on a scale of 0-5:

ltem

- Get out of the bed
- Visit family/friends
- Dress your lower body
- Run laundry washing machine
- Use knife/fork (spoon)
- Sit down from standing
- Go to a hospital
- Rub lotion on body
- Move a chair
- Get money from cash point (ATM)
- Bend and pick up something
- Do the cooking
- Throw object (e.g. ball)
- Use both dustpan and brush
- Do the shopping
- Clean a toilet
- Vacuum
- Get in or get out of the bathtub
- Walk upstairs with bag
- Walk on uneven ground
- Walk up hill
- Walk up 3 stairs
- Stand from squat
- Stand on 1 leg
- Walk outdoors >1km
- Lift heavy objects (10kg)
- Stand for hours
- Run
- Н

Appendix C: Brief Pain Inventory (BPI)

4 Items are scored from 0 'no pain' to 10 'pain as bad as you can imagine'

1 item is scored 0% 'no relief' to 100% 'complete relief' regarding how much relieve pain treatments or meications provided.

7 items ar rated from 0 'does not interfere' to 10 'completely interferes' regarding pain interference.

1903 ASE USE CK INK PEN	Da Su Str	te: (month) bject's Initial udy Subject	/ (day) / [) (y	rear)	Study Na Protocol PI: Revision:	#: 07/01/05			
7. What	treatn	nents or ma	edications	are you		g for your	pain?			
8. In the mark t 0% 1 No Relief	last 2 he bo 0%	4 hours, ho x below the 20%	ow much i e percenta 30%	relief hav age that r 40%	ve pain tre most sho 50%	eatments ws how m 60%	or medica nuch relia 70%	ations pro of you hav 80%	90%	lease ed. 100% Complete Relief
9. Mark f with ye A. Gen 0 Does Not Interfere	the bo our: eral /	x beside th Activity 2	e number (that desc	ribes how	, during th	e past 24	hours, pai	in has inte	10 Completel Interferes
B. Moo 0 Does Not Interfere	od 1	2	□3	4	5	6	7	8	9	Completel
C. Wall 0 Does Not Interfere	king (□3	4	5	6	7	8	9	Complete Interferes
D. Nor 0 Does Not Interfere	mai v	vork (incl 2	udes bo				me and 7	nousew 8	ork) 9	Complete Interferes
Does Not Interfere		2		4	5	6	7	8 []	9	Complete Interferes
0 Does Not Interfere	1 oyme	2 nt of life	3	4	5	6	7	8 []	9	Complete Interferes
0 Does Not Interfere	1	2	3	4	5	6	7 []	8 🗌	9	Completel Interferes
Page 2 of 2	2		с	opyright 199 Pair Al	1 Charles S. n Research G I rights reserv	Cleeland, Phi roup red	D			

Appendix D: Multidimensional Assessment of Interoceptive Awareness (MAIA-2) 37 items are rated from 0 'never to 5 'always'

Below you will find a list of statements. Please indicate how often each statement applies to you generally in daily life.

	C	ircle o	each line			
	Neve	r				Always
1. When I am tense I notice where the tension is located in my body.	0	1	2	3	4	5
2. I notice when I am uncomfortable in my body.	0	1	2	3	4	5
3. I notice where in my body I am comfortable.	0	1	2	3	4	5
4. I notice changes in my breathing, such as whether it slows down or speeds up.	0	1	2	3	4	5
5. Lignore physical tension or discomfort until they become more severe.	0	1	2	3	4	5
6. I distract myself from sensations of discomfort.	0	1	2	3	4	5
7. When I feel pain or discomfort, I try to power through it.	0	1	2	3	4	5
8. I try to ignore pain	0	1	2	3	4	5
9. I push feelings of discomfort away by focusing on something	0	1	2	3	4	5
 When I feel unpleasant body sensations, I occupy myself with something else so I don't have to feel them. 	0	1	2	3	4	5
11. When I feel physical pain, I become upset.	0	1	2	3	4	5
12. I start to worry that something is wrong if I feel any discomfort.	0	1	2	3	4	5
13. I can notice an unpleasant body sensation without worrying about it.	0	1	2	3	4	5
14. I can stay calm and not worry when I have feelings of discomfort or pain.	0	1	2	3	4	5
15. When I am in discomfort or pain I can't get it out of my mind	0	1	2	3	4	5
16. I can pay attention to my breath without being distracted by things happening around me.	0	1	2	3	4	5
17. I can maintain awareness of my inner bodily sensations even when there is a lot going on around me.	0	1	2	3	4	5
 When I am in conversation with someone, I can pay attention to my posture. 	0	1	2	3	4	5

	Neve r			Alwa ys		
19. I can return awareness to my body if I am distracted.	0	1	2	3	4	5
20. I can refocus my attention from thinking to sensing my body.	0	1	2	3	4	5
21. I can maintain awareness of my whole body even when a part of me is in pain or discomfort.	0	1	2	3	4	5
22. I am able to consciously focus on my body as a whole.	0	1	2	3	4	5
23. I notice how my body changes when I am angry.	0	1	2	3	4	5
24. When something is wrong in my life I can feel it in my body.	0	1	2	3	4	5
25. I notice that my body feels different after a peaceful experience.	0	1	2	3	4	5
26. I notice that my breathing becomes free and easy when I feel comfortable.	0	1	2	3	4	5
27. I notice how my body changes when I feel happy / joyful.	0	1	2	3	4	5
28. When I feel overwhelmed I can find a calm place inside.	0	1	2	3	4	5
29. When I bring awareness to my body I feel a sense of calm.	0	1	2	3	4	5
30. I can use my breath to reduce tension.	0	1	2	3	4	5
31. When I am caught up in thoughts, I can calm my mind by focusing on my body/breathing.	0	1	2	3	4	5
32. I listen for information from my body about my emotional state.	0	1	2	3	4	5
33. When I am upset, I take time to explore how my body feels.	0	1	2	3	4	5
34. I listen to my body to inform me about what to do.	0	1	2	3	4	5
35. I am at home in my body.	0	1	2	3	4	5
36. I feel my body is a safe place.	0	1	2	3	4	5
37. I trust my body sensations.	0	1	2	3	4	5

.

How often does each statement apply to you generally in daily life? Circle one number on each line
